Statistical Analysis Plan for clinicaltrials.gov

Official Title: Digital Mental Health Service for Non-Treatment Seeking Young Adults

NCT Number: NCT04948268

Grant Number: R34MH124960

Northwestern University Social and Behavioral Institutional Review Board Number: STU00214822

Statistical Analysis Plan

Aim 2. Feasibility

The primary aim of this study will be to evaluate the feasibility of conducting a larger SMART trial. Feasibility will be determined by:

1. meeting recruitment and enrollment goals;
2. obtaining at least 80% of follow up self-report data at primary endpoints; and
3. maintaining dropout below 30% across treatment conditions.

Descriptive statistics will be used to summarize recruitment, retention, completeness of self-report measures, and patterns of missing data. These analyses will inform the suitability of procedures for a future fully powered trial.

Aim 2a. Effectiveness of messaging interventions relative to active control

To evaluate the effects of the adaptive and randomized messaging interventions relative to the control condition, we will model trajectories of the primary outcome (psychological distress; K10) and secondary outcomes (PHQ-9, GAD-7, DSI-SS, and CB-RSS). For each outcome, we will estimate a generalized linear mixed model (GLMM) with one model per outcome, fixed effects for treatment arm, time, and the treatment by time interaction, a participant-level random intercept, an autoregressive correlation structure for repeated observations, and an identity link for normally distributed outcomes, with alternative link functions used as appropriate based on distributional properties. The primary inference will focus on the treatment by time interaction to determine whether either intervention produces a different rate of change over time compared to control. Secondary models will control for baseline demographic covariates (e.g., age, sex, race, ethnicity).

Controlling for missing data and bias. Should more than 5% of the outcome data be missing, we will examine the data for missing mechanisms and use multiple imputation rather than complete case analysis for the primary analysis to avoid bias, combining results from 5 imputed datasets using “mice”.

Aim 2b. Effectiveness of adaptive versus randomized messaging

If the treatment by time interaction indicates a significant difference between at least one messaging intervention and the control group for a given outcome ($p < .05$), as described in 2a, we will compare the adaptive and randomized messaging interventions for that outcome using the same GLMM approach, restricted to the 2 treatment arms. Outcomes will include the primary clinical outcome measure (K10) and secondary outcome measures (PHQ-9, GAD-7, DSI-SS, CB-RSS). The second primary outcome, engagement duration (time from first message received to last participant interaction), will be summarized descriptively by reporting means and standard deviations, and will be further explored using distribution-appropriate comparisons, as needed.

Aim 2c. Effectiveness of coaching for early disengagement

Participants in the intervention arms who meet predefined criteria for disengagement during the first 2 weeks will be re-randomized to receive coaching or continue without coaching. Analyses will use the same GLMM methods described in Aim 2a incorporating coaching as a covariate to explore whether coaching improves: engagement outcomes (engagement duration, response percentage, number of URL clicks), outcomes (K10, PHQ-9, GAD-7, DSI-SS, CB-RSS). Given the limited statistical power for this embedded re-randomization, results will be summarized descriptively, reporting model coefficients and confidence intervals rather than conducting formal hypothesis tests.

Aim 2d. Exploratory predictors of early disengagement

The need for coaching will be defined as meeting the disengagement criterion during the first 2 weeks. We will compare baseline demographic, clinical, and attitudinal variables between participants who do and do not meet this criterion. Continuous variables will be compared using the Wilcoxon rank sum test, and categorical variables will be compared using Pearson's chi squared test or Fisher's exact test when expected cell counts

are small.

In addition, exploratory predictive models such as random forests will be considered to evaluate whether combinations of baseline variables can classify participants who are likely to disengage early. These analyses are exploratory and intended to generate hypotheses for future trials.

Aim 3. Experimental therapeutics modeling

We will explore whether engagement targets (engagement) and psychological targets (coping skill use; CB-RSS) mediate treatment effects on psychological distress outcomes (K10) and secondary outcomes (PhQ-9, GAD-7, DSI-SS). Mediation analyses will be conducted only if the necessary preconditions for mediation are met (e.g., a significant effect of intervention condition(s) on the outcome (Aims 2a-2c), and a significant effect of intervention condition(s) on the proposed target (engagement or coping skill use; CB-RSS)).

If these conditions are met for an outcome/target pair, we will use generalized linear models to estimate paths a (intervention to target) and b (target to outcome) using appropriate link functions based on variable distributions. Mediation will be evaluated using the Iacobucci method, which constructs a normally distributed test statistic from standardized regression coefficients. Because these analyses are exploratory and involve multiple parallel models, we will control the false discovery rate (FDR) using the Benjamini-Hochberg procedure, with an FDR threshold of 10% appropriate to pilot mediation work. If the prerequisite conditions are not met for a given mediator or outcome, mediation models for that pair will not be estimated.

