We will partner with Mental Health America (MHA), the nation's largest mental health advocacy organization, to design and pilot a highly personalized messaging intervention for depression and anxiety. We will use an iterative design and development process that provides a voice to end-users in message and content creation.²⁵ We will pilot our automated, adaptive DMHI against a randomized version of the intervention and against an active control using a sequential multiple assignment randomized treatment (SMART) design, which targets those disengaged users for additional human support. The *adaptive intervention* will be powered by reinforcement learning to deliver tailored SMS messages based on user profiles and the ways in which a user interacts with the intervention system, along with links to longer psychoeducational content. The *randomized intervention arm* will not personalize the messages, but will still be an active treatment. The *active control* will provide, via a URL, brief psychoeducational content, but will not include the messaging component.

This project has the following three overarching aims:

Aim 1. Develop an adaptive messaging service for young adults that personalizes messages and psychoeducational content to the needs and preferences of an individual.

Aim 2. Evaluate the feasibility of conducting a SMART trial in which 120 young adults screening positive for depression or anxiety on the MHA website will be randomized to receive the adaptive (personalized) messaging intervention, a randomized version of the intervention, or an active control condition. Participants who meet criteria for non-engagement with the messaging interventions during the first 2 weeks will be randomized to receive coaching or continue without coaching for the remaining treatment period. Feasibility criteria include successful recruitment of participants, attaining 80% completion of research assessments, and <30% treatment dropout in at least one treatment condition. We will pilot the following analyses:

Aim 2a. Evaluate the effectiveness of messaging interventions, compared to waitlist control, in reducing psychological distress and secondary outcomes (depression and anxiety symptom severity, suicidal ideation, openness to therapy, and interest in formal treatment), and engaging treatment targets (subjective and objective engagement, behavioral activation, dysfunctional attitudes, coping skill use).

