Coaching involves human provisioned support, typically delivered by telephone or messaging (e.g., email or text). Coaching is believed to work in part by establishing a relationship that provides support and accountability.³⁸ A large number of studies have demonstrated that coaching improves both intervention use²⁰ and mental health outcomes.²⁹ While we expect that our messaging intervention will be engaging, we must also anticipate that there will be a group of users who will not engage. We therefore will explore the potential benefit of adding coaching to our messaging platform. Among those randomized to receive a messaging intervention, participants who become disengaged during the first 2 weeks of the intervention, will be re-randomized at the time they are determined to have disengaged to receive either (a) coaching, to help support engagement, in addition to continued randomized or adaptive messaging, or (b) continued adaptive or randomized messaging via SMS without coaching, depending on the participant's original intervention assignment.

Disengagement will be defined as 3 or more non-continuous days of not responding to messages, rating messages, or completing symptom assessments. Any single action will be considered evidence of continued engagement.

Treatment Arms:

Adaptive Intervention: The adaptive intervention will be powered by reinforcement learning to deliver tailored SMS messages based on user profiles and the ways in which a user interacts with the intervention system, along with links to longer psychoeducational content.

Randomized Intervention: The randomized treatment will use the same intervention as the Adaptive Intervention, except that it will not use machine learning for personalization.

[figure not shown]
Active Control (AC): In the Active Control group participants will receive psychoeducational text messages, (up to 3 on each of the 11 psychological strategies), but these messages will not include interactive messaging (i.e., messages that require a response or action from the user other than reading or clicking on a link to learn more about a particular psychological strategy). Some messages will contain a URL link that contains information about psychological strategies that may be helpful for managing symptoms of depression and anxiety proposed messaging interventions.

Clinical Trial Design:

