The clinical trial will utilize a SMART trial design (see Figure below). Participants will be recruited from MHA's website. The first level of randomization is to one of the three treatment conditions: (1) active control (n=40), adaptive intervention (n=40), or randomized intervention (n=40). This level of randomization will provide us with preliminary data on 1) the effectiveness of messaging as an

intervention and 2) the effectiveness and engagement of randomized vs. adaptive versions. The second level of randomization occurs following disengagement (as defined above under "Coaching" within the first two weeks of intervention use). Participants who meet the disengagement criteria from either the randomized or adaptive intervention will immediately be randomized to receive coaching or continue as self-guided. This data will provide us with preliminary information on the need for and value of coaching (Figure below).

Figure. SMART Trial Design

User feedback: When a participant concludes the intervention (up to 10 participants from each treatment combination [e.g., randomized intervention no coaching; randomized intervention + coaching; adaptive intervention no coaching; adaptive intervention + coaching]), they will be asked to engage in a 30-45-minute user feedback interview, to identify problems and deficiencies with the aim of improving the intervention. Participants who discontinue the intervention will be contacted for an interview at the time their discontinuation is confirmed.

Assessment Strategy:

The primary outcome is psychological distress, measured using the Kessler Psychological Distress Scale (K10).⁴⁹ Administration will occur as part of the research protocol via REDCap online. The primary intervention target is engagement length, measured by time from 1st message sent to the last data point obtained via SMS. Secondary outcomes include: depression, measured by the PHQ-9;³⁹ anxiety, measured by the GAD-7;⁵⁰ suicidal ideation, measured by the DS1-SS;^{51,52} and openness to seeking psychological care, measured by the Attitudes Toward Seeking Professional Psychological Help Scale-Short Form (ATSPPH-SF).⁵³

Data will be gathered from patients as outlined in the table below.

Table of Study Assessments and Assessment points

Construct	Measures	Brief Description	Screening	Study Week						
				0	1	4	8	12	16	

PROTOCOL TITLE: Digital Mental Health Service for Non-Treatment Seeking Young Adults

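### The dropout criterion for feasibility differs between protocol (any one condition below 30%) and SAP (below 30% across conditions), so the same data can pass one and fail the other

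*SAP*

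**What the plan says.** The SAP, under Aim 2 (Feasibility), states: "The primary aim of this study will be to evaluate the feasibility of conducting a larger SMART trial". It continues with "Feasibility will be determined by" and lists three items joined by *and*: recruitment and enrolment goals, at least 80% of follow-up self-report data at primary endpoints, and "maintaining dropout below 30% across treatment conditions".

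The protocol's Aim 2 also has three criteria, on recruitment, 80% completion of assessments and dropout. Its dropout criterion reads "<30% treatment dropout in at least one treatment condition".

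Neither document defines dropout for this purpose or gives it a time point. The protocol speaks of treatment dropout, the SAP only of dropout. Two related ideas appear in protocol section 8.1, and neither is tied to the criterion:

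- The trigger for re-randomization to coaching: "Disengagement will be defined as 3 or more non-continuous days of not responding to messages", with rating messages and completing symptom assessments also counted as engagement.
- Confirmed discontinuation, which prompts a feedback interview: "Participants who discontinue the intervention will be contacted for an interview at the time their discontinuation is confirmed".

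Usage also varies on which arms count. Protocol section 8.1 lists the active control under its treatment arms and says "The first level of randomization is to one of the three treatment conditions". SAP Aim 2b speaks of two treatment arms, meaning the messaging arms, and the protocol's list of treatment combinations for user feedback names only messaging arms with and without coaching.

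**The concern.** The protocol rule is met as soon as any one condition is below 30%. The SAP rule asks for more, whether it is read as every condition or as the pooled proportion. These are different decision rules for one item of a three-item test that settles the SAP's declared primary aim. With both in force, the trial could be called feasible under one document and not feasible under the other from identical data, and the rule could be chosen after dropout by arm is known. The undefined event and the unclear set of arms leave further room for that choice.

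**Working it through.** **Inputs.** Arm size is 40 in each of three arms (protocol sections 3.0 and 8.1). The threshold is strictly below 30% (both documents). Neither document gives an expected dropout rate, so there is no dropout figure to reproduce. The power statement attached to the arm size (80% at d = 0.64 with 40 per group) does reproduce: 80.7% by the noncentral t, assuming two-sided alpha of 0.05. The point uses only the 40.

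**Step 1: counts that meet the threshold.**
- One arm: 0.30 × 40 = 12, so at most 11 dropouts.
- Two arms pooled: 0.30 × 80 = 24, so at most 23.
- Three arms pooled: 0.30 × 120 = 36, so at most 35.

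**Step 2: one dataset, no assumed rate.** Take dropouts of 10/40 and 16/40 in the messaging arms and 12/40 in control.
- Protocol rule: 10/40 = 25%. Met, whether two or three arms count.
- SAP, each arm: 16/40 = 40%. Not met.
- SAP, two messaging arms pooled: 26/80 = 32.5%. Not met.
- SAP, three arms pooled: 38/120 = 31.7%. Not met.

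**Step 3: direction.** If the same arms and the same event are used, a pooled proportion below 30% means that the lowest arm is below 30%, and so does every arm being below 30%. Hence any data that meet the SAP rule meet the protocol rule. Checking all 41² = 1,681 two-arm and 41³ = 68,921 three-arm outcomes found no exception.

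**Step 4: how often the verdicts differ.** Assume independent arms with a common true dropout rate p, and let P = P(X ≤ 11 | n = 40, p). For k arms:
- at least one arm: 1 − (1 − P)^k
- each arm: P^k
- pooled: P(X ≤ 23 | 80, p) for k = 2, or P(X ≤ 35 | 120, p) for k = 3

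Because the SAP rule is nested in the protocol rule, the chance of differing verdicts is the first probability minus the relevant SAP one. Worked case at p = 0.30, k = 2: P = 0.4406; at least one = 1 − 0.5594² = 0.687; pooled = 0.458; each = 0.4406² = 0.194. The differences are 0.229 and 0.493.

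| k | p | P | At least one | Pooled | Each | Differ (pooled) | Differ (each) |
|---|---|---|---|---|---|---|---|
| 2 | 0.20 | 0.9125 | 0.992 | 0.978 | 0.833 | 0.014 | 0.160 |
| 2 | 0.25 | 0.7151 | 0.919 | 0.818 | 0.511 | 0.101 | 0.407 |
| 2 | 0.30 | 0.4406 | 0.687 | 0.458 | 0.194 | 0.229 | 0.493 |
| 2 | 0.35 | 0.2053 | 0.368 | 0.145 | 0.042 | 0.223 | 0.326 |
| 3 | 0.20 | 0.9125 | 0.999 | 0.994 | 0.760 | 0.005 | 0.240 |
| 3 | 0.25 | 0.7151 | 0.977 | 0.876 | 0.366 | 0.101 | 0.611 |
| 3 | 0.30 | 0.4406 | 0.825 | 0.466 | 0.086 | 0.359 | 0.739 |
| 3 | 0.35 | 0.2053 | 0.498 | 0.106 | 0.009 | 0.392 | 0.489 |

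Between the tabulated rates the pooled two-arm difference goes slightly higher (0.248 at p = 0.32).

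**The case against.** The strongest reply is that little hangs on the 30% line. Feasibility is assessed with descriptive statistics meant to inform a future trial. No hypothesis test, stopping rule or sample size depends on it, and protocol section 3.0 offers an effect-size benchmark (about d = 0.38) for deciding on a larger trial. Retention will be summarized anyway, and if it is shown by arm a reader can apply either rule. All of this stands and limits the severity. It does not remove the conflict, because the SAP says that these criteria determine its primary aim.

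The probabilities are also only illustrations. At a true rate of 20% with pooling, the verdicts differ in about 1% of trials, and the 74% needs three conditions, the each-arm reading and a true rate near 30%. That stands too; the conflict is shown by the counts in Step 2 alone.

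Three stronger readings are tempting and not supported:

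- **That the protocol's rule is too lenient and must go.** Nothing in the documents makes it invalid. For a pilot asking whether any version is worth taking forward it is defensible, and adopting it in both places would cure the defect.
- **That control plainly counts, so that control alone could satisfy the protocol rule.** Usage is mixed, as set out above. Control messages are also non-interactive, so a dropout measure based on responses would be hard to observe there.
- **That the SAP rule could be the easier one.** This needs different arms or events under the two rules. With matched inputs it cannot happen.

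**Conclusion.** The concern holds as an inconsistency between two current texts: the criterion is wrong as written because the documents give different pass rules for it. That rests on the wording and on 40 per arm, with no assumed dropout rate. Its likely size does depend on assumptions (independent arms, one common true rate). At 20, 25, 30 and 35% the range runs from about 1–23% of trials for two messaging arms pooled to 24–74% for three conditions with each arm required. The missing definition of dropout, its time point and the arms counted are part of the same defect. A reader might infer that the trial's effectiveness analyses are affected; they are not. It should be fixed, and SHOULD-FIX is a reasonable grade because the consequence is the feasibility label of a pilot.

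**What to change.** Put one identical criterion in protocol Aim 2 and in SAP Aim 2, item 3, for example: *Dropout, defined as [event] by [time point], below 30% in [at least one of / each of / pooled over] [the two messaging arms / all three conditions].* The choice in each bracket belongs to the sponsor. If data are already in, report dropout by arm, give the verdict under both published rules, and disclose the discrepancy.

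The cost is one aligned sentence in each document, including the definition of dropout. If the sponsor chooses each or pooled, the bar becomes harder to clear than under the protocol's present wording: at an assumed 25% dropout with two messaging arms, the chance of meeting it falls from 92% to 51% (each) or 82% (pooled). Keeping the at-least-one rule carries no such cost.

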Aim 2b. Evaluate the effectiveness of an adaptive vs. randomized messaging intervention to reduce psychological distress, increase engagement duration, improve secondary outcomes and targets.

Aim 2c. Evaluate the ability of coaching to improve engagement targets and psychological outcomes.

Aim 2d. Explore participant characteristics and factors associated with the need for human coaching support above and beyond a messaging intervention with randomized and adaptive messaging.

Aim 3: Experimental therapeutics: Explore if engagement targets (subjective and objective engagement) and psychological targets (behavioral activation, dysfunctional attitudes, coping skill use) mediate significant effects for distress observed in Aims 2a, 2b, or 2c.

BACKGROUND:

Most young adults with mental health diagnoses do not seek out in-person mental health care. While young adults are the age group with the highest prevalence (26.3%) of mental health problems, they are the adult age group with the lowest rates of treatment.²⁶ Without early intervention, their symptoms tend to become worse and more chronic.³⁻⁶ We know that digital mental health interventions are effective at reducing affective symptoms,^{15,16} and young people are interested in these interventions.²⁷

Young adults use digital technologies regularly: 96% own a smartphone, and they are the age group most likely to access the internet exclusively through their smartphone.²⁸ Thus, smartphones are a medium with high penetration through which to deliver a digital mental health intervention. Meta-analyses^{15,16,29} have consistently shown that mobile app and browser-based DMHIs can be effective at reducing symptoms of anxiety and depression across randomized controlled trials.²⁹ While DMHIs are effective when used, they often produce high dropout.^{20,21}

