N/A	Screener	Demographics, treatment history, message preferences, timing, topic interest, etc.	X						
Psychological Distress	*Kessler Psychological Distress Scale (K10)	10-item self-report measure of transdiagnostic distress	X		X	X	X	X	
Subjective engagement	Twente Engagement with eHealth Technologies Scale (TWEETS)	9-item self-report measure assessing cognitive, behavioral, and affective engagement with a digital tool		X	X	X	X	X	
Cognitive behavioral coping	***Cognitive Behavioral Response to Stress Scale (CB-RSS)	9-item self-report measure of behavioral and cognitive coping related skills		X		X	X	X	X
Depression symptoms	** Patient Health Questionnaire-9 (PHQ-9)	10-item self-report measure assessing depression symptom severity	X		X	X	X	X	
Generalized anxiety disorder symptoms	**Generalized Anxiety Disorder-7 (GAD-7)	8-item measure assessing GAD symptom severity	X		X	X	X	X	
Suicidal ideation	***Depression Symptom Inventory - Suicidality Subscale (DSI-SS)	4-item self-report questionnaire assessing the frequency and intensity of suicidal thoughts over previous two weeks		X		X	X	X	X
Openness to seeking psychological care	Attitudes Toward Seeking Professional Psychological Help Scale-Short Form (ATSPPH-SF)	10-item self-report measure assessing a) openness to seeking treatment for emotional problems and b) value and need		X		X	X	X	X

PROTOCOL TITLE: Digital Mental Health Service for Non-Treatment Seeking Young Adults

		in seeking treatment						
Supportive Accountability	Supportive Accountability Index (SAI) [NOTE THIS IS ONLY FOR PEOPLE RANDOMIZED TO COACHING]	A 6-item self-report measure that assesses elements of the supportive accountability model of human support in digital mental health treatments		X	X			
Cross cutting symptom severity inventory	DSM-5 Cross-Cutting Symptom Measure*	Brief Cross-Cutting symptom inventory assessing severity of different psychiatric symptoms	X	X	X			
Helpfulness and supportiveness of messages	Message Perceptions Questionnaire	A custom 6-item self-report measure of supportiveness and helpfulness of messages.		X	X			
Usability	USE	Usefulness, Satisfaction, and Ease of Use Questionnaire (USE)		X	X			
Disability, health, and impairment	WHODAS 2.0	12-question, self-administered questionnaire and generic assessment instrument for health and disability	X	X	X			
Social Anxiety Symptoms	BFNE	12-item self-administered questionnaire assessing fear of negative evaluation	X					

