13.0 Waivers and Alterations of Consent Information:

N/A

14.0 Financial Compensation:

DESIGN STUDY

Longitudinal Usability Testing

Wave 1 (8-week intervention):

Participants will be compensated \$20 for completing baseline measures and the initial set-up call, and \$20 for each subsequent assessment point (Week 4 & 8), and \$20 for each of the 2 interviews (Week 4 & 8). Amounting to a total potential earning of \$100 per participant. Compensation will be offered in the form of an electronic Amazon gift card or check.

Wave 2 (4-week intervention):

Participants will be compensated \$20 for completing the 4-week surveys, and \$20 for completing the 4-week interview. Amounting to a total potential earning of \$40 per participant. Compensation will be offered in the form of an electronic Amazon gift card or check.

CLINICAL TRIAL

We will reimburse all trial participants for completing research assessments. Participants will be compensated \$25 per major assessment session (Baseline, Week 4, 8, 12, 16; we note that a subjective engagement questionnaire will be administered to those in the intervention group at week 1, but due to brevity this is not considered a major assessment point). Amounting to a total potential earning of \$125 per participant. Compensation will be offered in the form of an electronic gift card or check.

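### The SAP plans no treatment-effect analysis for ATSPPH-SF (openness to seeking care), one of the protocol's four named secondary outcomes, and gives no reason

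*SAP*

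**What the plan says.** **Protocol.** The Assessment Strategy (Section 8.1, Clinical Trial) lists the secondary outcomes by instrument: PHQ-9 for depression, GAD-7 for anxiety, DSI-SS for suicidal ideation, and "openness to seeking psychological care, measured by the Attitudes Toward Seeking Professional Psychological Help Scale-Short Form (ATSPPH-SF". Aim 2a, in the statement of aims, asks for the effect of messaging against control on "secondary outcomes (depression and anxiety symptom severity, suicidal ideation, openness to therapy, and interest in formal treatment". Aim 2b asks whether adaptive rather than randomized messaging will "reduce psychological distress, increase engagement duration, improve secondary outcomes and targets". The Table of Study Assessments has a row for the scale, described as a "10-item self-report measure assessing a) openness to seeking treatment for emotional problems and b) value and need" in seeking treatment, and that row carries five marks. Section 14.0 pays participants "per major assessment session (Baseline, Week 4, 8, 12, 16", which is also five occasions.

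**SAP.** Aim 2a fits one mixed model per outcome to K10 and to "secondary outcomes (PHQ-9, GAD-7, DSI-SS, and CB-RSS". Aim 2b names K10 and "secondary outcome measures (PHQ-9, GAD-7, DSI-SS, CB-RSS", and starts only when a condition on Aim 2a is met: "If the treatment by time interaction indicates a significant difference between at least one messaging intervention and the control group for a given outcome". Aim 2c repeats the same five measures alongside engagement. Aim 3 names K10, PHQ-9, GAD-7 and DSI-SS as outcomes. The SAP never mentions ATSPPH-SF or openness to care, and it does not say that a protocol outcome has been removed.

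**The concern.** A secondary outcome that the protocol names and schedules has no analysis in the SAP. If the SAP is followed as written, the trial collects ATSPPH-SF repeatedly and estimates no treatment effect on it.

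This matters more here than for an incidental scale. The trial enrols young adults who are not seeking treatment, and Help Seeking is one of the 11 intervention strategies. ATSPPH-SF is the only scheduled instrument described as measuring openness to care. Whether messaging shifts that attitude is a stated Aim 2a and 2b question. The pilot is meant to inform a larger trial, which would begin without a planned estimate of it.

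There is also a reporting consequence. With the omission unexplained, a reader of the results cannot tell a planned removal from an oversight or from selective reporting. Any later ATSPPH-SF result would count as not pre-specified.

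**Working it through.** The plan states no figure on this point to reproduce. The check is a comparison of lists.

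| Measure | Protocol role | SAP 2a | SAP 2b | SAP 2c | SAP 3 |
|---|---|---|---|---|---|
| PHQ-9 | secondary outcome | yes | yes | yes | yes |
| GAD-7 | secondary outcome | yes | yes | yes | yes |
| DSI-SS | secondary outcome | yes | yes | yes | yes |
| ATSPPH-SF | secondary outcome | no | no | no | no |
| CB-RSS | coping target (proposed mediator) | yes | yes | yes | as mediator |

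Three of the four named secondary outcomes have a treatment-effect model and one of four has none. CB-RSS, which measures coping, takes the fourth secondary place in the SAP without explanation.

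**Could another part of the SAP cover it?**
- Aim 2d compares baseline attitudinal variables between participants who do and do not disengage early. It uses no follow-up scores and does not compare arms.
- Aim 2b's list is introduced in wording that could be read as open. Entry to Aim 2b for an outcome, however, requires a significant Aim 2a interaction for that outcome, and Aim 2a's list is closed. ATSPPH-SF cannot get there.

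**Are the data there to model?** The ATSPPH-SF row has five marks, in the same pattern as the DSI-SS row, and DSI-SS is modelled. Column positions in the extracted table are uncertain, but five marks fit the five major sessions in Section 14.0. The Aim 2a model would apply unchanged.

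**How precise would the missing estimate be?** As a guide, take one messaging arm against control at one visit, in SD units, without baseline adjustment. The 95% half-width is t × √(2/n).
- n = 40 per arm (planned): 1.991 × √(2/40) = 1.991 × 0.2236 = 0.445 SD.
- n = 32 per arm (assuming the 80% completion target, 0.80 × 40): 1.999 × √(2/32) = 1.999 × 0.25 = 0.500 SD.

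**What does adding it cost in false positives?** Aim 2a now has 5 outcomes (K10, PHQ-9, GAD-7, DSI-SS, CB-RSS) and would have 6. No multiplicity control is stated for Aim 2a; the false discovery rate procedure is stated only for Aim 3.
- One interaction test per outcome, independent: 1 − 0.95^5 = 0.226, rising to 1 − 0.95^6 = 0.265.
- Bonferroni upper bound for the same case: 5 × 0.05 = 0.25, rising to 6 × 0.05 = 0.30.
- Two arm-versus-control contrasts per outcome, independent: 1 − 0.95^10 = 0.401, rising to 1 − 0.95^12 = 0.460.

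The SAP's wording about either intervention differing from control fits the two-contrast reading at least as well. Positive correlation among the outcomes would be expected to lower the independent-test figures.

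**The case against.** The strongest reply is that the SAP narrowed the scope on purpose. It also names no model for behavioral activation or dysfunctional attitudes, both protocol targets, or for interest in formal treatment, the fifth secondary construct in protocol Aim 2a. On this view ATSPPH-SF is one of several measures set aside in a 120-person pilot whose primary aim is feasibility, and the data remain available for a later estimate. Deliberate narrowing cannot be ruled out. But behavioral activation and dysfunctional attitudes have no row in the assessment table, whereas ATSPPH-SF has a row with repeated measurement and is named as a secondary outcome. If it was dropped, neither document says so.

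Some narrower points stand:
- Protocol Aim 3 asks about mediation of effects on distress, so the absence of ATSPPH-SF from SAP Aim 3 is not a discrepancy.
- Protocol Aim 2c speaks of engagement targets and psychological outcomes, which need not include an attitude scale. The firm gap is in Aims 2a and 2b.
- The half-widths above are for a single-visit mean difference, not for the treatment-by-time interaction on which the SAP bases inference. They show the order of precision only.
- The lack of multiplicity control applies to every Aim 2a outcome, so it is no reason to treat ATSPPH-SF differently from the others.

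None of these supplies the missing analysis.

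**Conclusion.** The concern holds. One of the four secondary outcomes named in the protocol's Assessment Strategy has no treatment-effect analysis in the SAP, and no reason is given. Two stated questions are affected: messaging against control (Aim 2a) and adaptive against randomized messaging (Aim 2b), both for openness to care. The count of one in four rests on the list of instruments. Counted by construct in protocol Aim 2a, interest in formal treatment also has no named analysis, which widens the gap.

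The consequence is limited to this secondary outcome. What is lost is a pilot-level estimate, with a half-width of about 0.45 SD at 40 per arm or 0.50 SD at 32 per arm under the single-visit, unadjusted assumption. Repeated measures or baseline adjustment would narrow it. This should be corrected, but it does not threaten the trial's main conclusions.

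**What to change.** Add ATSPPH-SF to the secondary-outcome lists in SAP Aims 2a and 2b, using the same mixed model and the same Aim 2b entry condition. Adding it to Aim 2c, where results are already descriptive, is optional; Aim 3 needs no change. If the scale was dropped on purpose, record that instead as a dated, justified removal in both the protocol and the SAP. Whichever route is taken, the same note should state what became of interest in formal treatment.

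Report the ATSPPH-SF result as an estimate with a 95% confidence interval, labelled secondary, and carry that label to any Aim 2b comparison it opens. Doing the same for the other secondary outcomes would keep the plan uniform.

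The cost is one measure added to two lists (three with Aim 2c) and one more model per aim, on data already scheduled. It needs no new visits, forms or participants. The statistical price is one more unadjusted secondary outcome in Aim 2a, with the rise in false-positive risk shown above, and one more possible Aim 2b comparison.
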